2.3.5 Confirmed blood pressure decreases (CBPD)

The number and percentage of subjects who experience a confirmed blood pressure decrease requiring a study drug dose adjustment during study drug administration will be provided. Among subjects who experience a confirmed blood pressure decrease event, the events will be further characterized with respect to impact on study drug administration (dose decreased or

study drug discontinued or both), the timing of event onset relative to study drug initiation, the magnitude of the blood pressure decrease at its onset and the trough blood pressure recorded, the blood pressure measurements after study drug discontinuation, outcome, treatment(s) required, and whether considered symptomatic, i.e. an AE. In addition, these summaries will be provided separately for those confirmed events that resulted in study drug dose reduction, and those that resulted in study drug discontinuation.

Course of blood pressure after the occurrence of first CBPD up to Day 5 will be presented.

To further investigate the impact of CBPD, the following analyses will be performed.

- Baseline characteristics by CBPD subgroup (yes/no).
- Concomitant medications by CBPD subgroup (yes/no).
- CV death through Day 180, WHF through Day 5 and CV death or rehospitalization due to heart failure or renal failure through Day 180 by CBPD impact on study drug administration (dose decreased or study drug discontinued or both).
- AEs associated with the occurrence of the CBPD.

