# 7 Safety monitoring

## 7.1 Adverse events

An adverse event (AE) is any untoward medical occurrence (i.e., any unfavorable and unintended sign [including abnormal laboratory findings], symptom or disease) in a subject or clinical investigation subject *after providing written informed consent* for participation in the study. Therefore, an AE may or may not be temporally or causally associated with the use of a medicinal (investigational) product. In this study, non-serious AEs will be collected through Day 5, serious adverse events (SAEs) will be collected through Day 14.

The occurrence of adverse events should be sought by non-directive questioning of the patient at each visit during the study. Adverse events also may be detected when they are volunteered by the patient during or between visits or through physical examination, laboratory test, or other assessments.

Abnormal laboratory values or test results constitute adverse events only if they fulfill at least one of the following criteria:

- they induce clinical signs or symptoms,
- they are considered clinically significant,
- they require therapy.

Unexpected, clinically significant abnormal laboratory values or test results should be identified through a review of values outside of normal ranges/clinically notable ranges, significant changes from baseline or the previous visit, or values which are considered to be non-typical in

patient with underlying disease. Investigators have the responsibility for managing the safety of individual patient and identifying adverse events. Alert ranges for labs and other test abnormalities are included in Section 14 [Appendix 1](#).

Adverse events with an onset up to and including Day 5 should be recorded in the Adverse Events CRF under the signs, symptoms or diagnosis associated with them accompanied by the following information.

- the severity grade
  - mild: usually transient in nature and generally not interfering with normal activities
  - moderate: sufficiently discomforting to interfere with normal activities
  - severe: prevents normal activities
- its relationship to the study treatment (no/yes),
- its duration (start and end dates) or if the event is ongoing an outcome of not recovered/not resolved should be reported.
- whether it constitutes a serious adverse event (SAE)
- action taken regarding study treatment
- whether other medication or therapies have been taken (concomitant medication/non-drug therapy)

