Detailed AE listings will also be provided.

In addition, AEs representing identified and potential safety risk in addition to events of interest will be grouped. The incidence (absolute and relative frequency) of each potential risk will be summarized by treatment group. Odds ratios and associated 95% confidence intervals comparing serelaxin with placebo will be presented using the Mantel-Haenszel test. In addition, subjects experiencing each of these risks will be listed. Such safety risks and events of interest are displayed in below table.

Table 2-7 Safety risk and event of interest search specification

Type of Risk	Specification
Safety risk	
Hypotension	Search terms include the following PTs: Blood pressure ambulatory decreased Blood pressure decreased Blood pressure diastolic decreased Blood pressure immeasurable Blood pressure orthostatic decreased Blood pressure systolic decreased CT hypotension complex Diastolic hypotension Dizziness postural Hypotension Mean arterial pressure decreased Neonatal hypotension Orthostatic hypotension Procedural hypotension Altered state of consciousness Blood pressure abnormal Blood pressure ambulatory abnormal Blood pressure diastolic abnormal Blood pressure fluctuation Blood pressure inadequately controlled Blood pressure orthostatic abnormal Blood pressure systolic abnormal Blood pressure systolic inspiratory decreased Consciousness fluctuating Depressed level of consciousness Dizziness Dizziness exertional Labile blood pressure Loss of consciousness Presyncope

Type of Risk	Specification
	Schellong test
	Syncope
	Tilt table test positive
Hemoglobin/ hematocrit transient decrease	SMQ 'Haemorrhages' (Broad) HLGT 'Anaemias nonhaemolytic and marrow depression'
Fetotoxicity and Teratogenicity	SMQ 'Haematopoietic erythropenia' (Broad) SMQ 'Pregnancy and neonatal topics' (Broad)
Event of interest	
Hypokalemia	Search terms include the following PTs: Alkalosis hypokalaemic Blood potassium abnormal Blood potassium decreased Hypokalaemia Hypokalaemic syndrome Hyperkaliuria Transtubular potassium gradient Urine potassium abnormal Urine potassium decreased Urine potassium increased
Menorrhagia/Metrorrhagia	HLGT 'Menstrual cycle and uterine bleeding disorders'
Potential promotion of cancers	SMQ 'Malignancies' (Broad)

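### SAP 2.3.5 treats AE status as the definition of a symptomatic confirmed blood pressure decrease, but under the protocol a symptom-free decrease can be an AE, so the share labelled symptomatic can be overstated

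*SAP*

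**What the plan says.** SAP 2.3.5 first counts subjects with a "confirmed blood pressure decrease requiring a study drug dose adjustment" during infusion. It then characterizes the events by effect on dosing, timing, size of the fall, trough pressure and later readings, and ends the list with "outcome, treatment(s) required, and whether considered symptomatic, i.e. an AE". No other definition of symptomatic is given. Protocol 10.5.2 says only that the events will be characterized further.

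Protocol 7.1 defines an AE broadly, as "any unfavorable and unintended sign [including abnormal laboratory findings], symptom or disease". For one class of finding it adds a restriction: "Abnormal laboratory values or test results constitute adverse events only if they fulfill at least one of the following criteria". The three criteria are "they induce clinical signs or symptoms", "they are considered clinically significant" and "they require therapy".

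Protocol 6.5.1 includes systolic and diastolic pressure in the abbreviated physical examination. Significant findings up to Day 5 that meet the AE definition go on the AE page. Under Protocol Table 5-4 a decrease is confirmed by two readings 15 minutes apart; symptoms play no part.

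**The concern.** The SAP uses one attribute (reported as an AE) as if it were another (the patient had symptoms). The protocol does not make them the same. Take a decrease that is confirmed on two readings, leads to the infusion being stopped and is treated, in a patient with no complaint. A site may properly record this as an AE of hypotension, and the SAP rule then counts it as symptomatic.

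Hypotension is the first safety risk in SAP Table 2-7, and Protocol 3.1 gives it as the reason for regular pressure monitoring during infusion. A reader of the study report will take a symptomatic count at face value. As defined, the count mixes symptoms with how readily sites file AEs. It also blurs two items that the SAP means to keep apart: treatment required has its own place in the same list, yet the need for treatment can be the reason the event was filed as an AE.

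**Working it through.** The documents give no figure to reproduce. The check is a comparison of texts, followed by the direction of the error.

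**Can a symptom-free CBPD be an AE?**

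1. A CBPD is defined by readings alone (Protocol Table 5-4), so it can occur without symptoms.
2. A fall in pressure is a sign, and the general definition in Protocol 7.1 accepts an unfavorable sign without a symptom.
3. Protocol 6.5.1 confirms this for pressure found at the physical examination: what decides recording is significance and the AE definition, not a complaint.
4. The three-criteria list in Protocol 7.1 names laboratory values and test results, and blood pressure sits under vital signs (6.5.2). The argument therefore does not rest on that list. If a site applies it to pressure by analogy, the second and third criteria need no symptom.
5. Protocol 3.1 allows the investigator to take measures against the fall between the two readings, so a treated, symptom-free decrease is realistic.
6. Neither document limits AE reporting of pressure decreases to symptomatic ones.

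The answer is yes.

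**Direction.** Let s be the truly symptomatic share of CBPDs, q the share of symptom-free CBPDs reported as AEs, and r the share of symptomatic CBPDs with an AE linked to the event.

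- Share labelled symptomatic = s·r + (1 − s)·q.
- With r = 1 this is s + (1 − s)·q, which is never below s.
- With r < 1 the label is too high only if (1 − s)·q > s·(1 − r).

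**Illustration.** All values are assumed. With s = 20% and r = 1:

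| q | Share labelled symptomatic |
|---|---|
| 0% | 0.20 + 0.80 × 0 = 20% |
| 10% | 0.20 + 0.80 × 0.10 = 28% |
| 50% | 0.20 + 0.80 × 0.50 = 60% |
| 100% | 0.20 + 0.80 × 1 = 100% |

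With s = 20%, q = 10% and r = 60%, the label gives 0.12 + 0.08 = 20%. The total then equals the true share although some events are misclassified each way.

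**Between arms.** Let the arms have N₁ and N₀ CBPDs and the same s, q and r. The labelled share is s·r + (1 − s)·q in both, and the ratio of labelled counts is N₁/N₀, the same as the ratio of truly symptomatic counts. With r = 1 the absolute difference in counts changes from (N₁ − N₀)·s to (N₁ − N₀)·[s + (1 − s)·q]. A difference in share arises only if s, q or r differs by arm.

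**The case against.** The strongest reply is that the wording is loose but other output covers the gap. SAP 2.3.5 reports treatment separately and ends with an item on AEs linked to the CBPD. SAP 2.3.1 tabulates AEs by preferred term and lists each with its verbatim term and its start and stop times. A reader could then tell syncope from a low reading. The same section plans outcomes by the effect of the CBPD on dosing, so the symptomatic share is not the only evidence on harm. All this is true and limits the consequence. It does not correct the labelled count. The Table 2-7 hypotension group does not correct it either, because it pools pressure terms with symptom terms, as in "Dizziness exertional Labile blood pressure Loss of consciousness Presyncope".

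A second reply is that the eCRF and its completion instructions are not in the documents. They may hold a symptom field, or direct sites to file an AE only when a decrease is symptomatic. This stands, and it is why the error is stated as possible and not certain.

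Three stronger readings are tempting, and the documents do not support them.

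- *Overstatement is certain.* It is not: there is none if q = 0, and symptoms filed under an unlinked term pull the other way.
- *The error falls mainly on serelaxin.* Protocol 3.6 makes more decreases on serelaxin plausible, but more events do not bias the share, and investigators are blinded (Protocol 5.4). Only the absolute count difference grows.
- *The dose change shows that the investigator judged the event significant.* Table 5-4 requires the change from readings alone, so it records no such judgement.

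**Conclusion.** The point holds in a limited form. SAP 2.3.5 states a classification rule that disagrees with the protocol's AE definition, and a symptom-free CBPD reported as an AE would be labelled symptomatic. If symptomatic events are all reported and linked, the error can only raise the labelled share. Its size depends on site reporting practice and eCRF content that the documents do not show, so the percentages above illustrate the mechanism and are not estimates.

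One descriptive safety attribute is affected. Counts of CBPDs, the AE tables and the efficacy analyses are not. The correction is still worth making, because the attribute describes the first-listed safety risk and would be read literally.

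**What to change.** In SAP 2.3.5, drop the word symptomatic from this item and report it as *CBPD reported as an AE*. Add a separate row, *CBPD with a recorded symptom*, derived as follows:

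- from an eCRF symptom field for these events, if one exists;
- otherwise from associated AEs whose preferred term is a symptom already in Table 2-7 (the dizziness terms, presyncope, syncope, and altered, depressed or lost consciousness). Terms that describe only the pressure do not qualify.

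State the time window in the SAP. It should include symptoms that begin shortly before the confirming reading, and it could end with the five-hour post-event monitoring in Protocol 6.5.2.

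State also that the second row is a lower bound. Protocol 7.1 lets sites enter an AE as a sign, a symptom or a diagnosis, so dizziness recorded only as hypotension would be missed. The row must not be presented as the true symptomatic rate. Keeping both rows shows the reader the two quantities side by side.

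The cost is one revised SAP sentence and one derived flag. AE terms and start times are already specified for the listings in SAP 2.3.1, so no new data collection is needed.

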### **3.6 Risks and benefits**

Dyspnea and congestion are the cardinal presenting features of AHF. The rapid onset or change in signs and symptoms of HF requires urgent care. Hospitalization and worsening heart failure with accompanying end organ damage, namely, worsening renal function and myocardial wall stress and injury, are both associated with increased mortality. Although therapies are available to improve dyspnea and congestion in AHF, a substantial number of patients remain symptomatic prior to discharge. Importantly, no AHF therapy to date has demonstrated a mortality benefit.

Serelaxin infused for 48 hours in both the pre-RELAX-AHF ([Teerlink et al, 2011](#)) and RELAX-AHF study ([Teerlink et al, 2013](#)) demonstrated significant improvement in dyspnea and signs and symptoms of congestion. It was also associated with significant reductions in early worsening heart failure events and length of stay during the index hospitalization including duration of intensive care. Reductions in both cardiovascular and all-cause mortality were observed in the serelaxin-treated patients in RELAX-AHF. Pre-specified biomarker changes suggest serelaxin therapy has a protective effect on both the heart and kidney, supporting the mortality benefit. Serelaxin was generally well-tolerated with no notable differences in the overall adverse event profile compared to placebo. Although blood pressure can decrease in a portion of patients due to the vascular mechanism of action of the drug, worse outcomes were not observed in these patients. The current instructions for the management of systolic blood pressure (SBP), including close and careful monitoring as well as mandatory dose adjustment or stopping rules, which were utilized during RELAX-AHF, support that current safety rules and management of SBP are both robust and sufficient.

The risk to patients participating in study will be minimized by compliance with the inclusion/exclusion criteria and close clinical monitoring, which proved effective during the RELAX-AHF trial. Since the potential of immunogenicity as a result of repeated intravenous dosing has not yet been fully characterized, those patients who participated in prior serelaxin clinical studies will be excluded. It is also important to note that all patients in this study will

be required to receive standard-of-care background HF management during hospitalization as well as the follow-up period of 180 days.

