#### **5.5.4 Instructions for prescribing and taking study treatment**

The study drug infusion will begin after the signing the ICF and the completion of all screening procedures, and continue for 48 hours. Study drug should be administered in a dedicated IV line or port, as soon as possible, but no more than 4 hours after randomization. Serelaxin infusion solution must be prepared in infusion bags containing 5% dextrose as a diluent. Recommended infusion bags, which have been tested and qualified for use with serelaxin, are listed in [Table 5-1](#).

However, there is no restriction for use of any other 250 mL infusion bag with 5% dextrose.

Compatible infusion filters, which have been tested and qualified for use with serelaxin, **must** be used to administer the study drug. [Table 5-2](#) lists the infusion filters that can be used for this study.

For each randomized patient to receive the study drug according to a weight-range adjusted dosing regimen over a period of 24 hours ([Table 5-3](#)), the required amount of study drug will be withdrawn from the 6-mL vials (with 3.5 mL fill) contained in the blinded kits, taking care not to shake the vial, injected into a 250 mL intravenous bag of 5% dextrose solution recommended above, and then infused at a constant rate of 10 mL/hour. Details of study drug preparation and infusion can be found in the *Pharmacy Manual*.

Study drug will be dispensed only by study staff qualified to perform that function under applicable local laws and regulations for the study site(s), according to the protocol and Schedule of Events (see [Table 6-1](#)). The blinded study drug kits, allocated to each randomized patient via IRT, containing one 6-mL vial of serelaxin or placebo (with 3.5 mL fill), will be used to compound study drug for the first 24 hour of infusion for all patients <115 kg in weight; in cases when the subject is  $\geq$ 115 kg, two study drug kits will be assigned via IRT for the first 24 hour of infusion. The body weight determined between presentation and randomization, rounded up to the nearest 0.5 kg, will be used for the calculation of the dose for each patient, for the entire 48 hour infusion period. Study drug from a second kit or pair of kits, also assigned via IRT depending on the patient's body weight as assessed between presentation and randomization, will be used to continue the infusion for the second 24 hours.

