**Table 5-4 Dosing adjustment of study drug administration in the event of systolic BP decrease**

Changes in systolic BP during infusion*	Adjustments of study drug administration
Decrease >40 mmHg from pre-treatment at baseline, but systolic BP remains $\geq$ 100 mmHg	Reduce the infusion rate by half for the remainder of the study drug administration, i.e., reduce infusion rate from 10 mL/hour to 5 mL/hour for the remainder of 48-hour infusion
Decrease in absolute systolic BP to <100 mmHg	Permanently terminate study drug infusion

\* These systolic BP values should be confirmed by two measurements taken 15 minutes apart

In addition, dosing may be discontinued at any time at the discretion of the investigator. Reasons the investigator may discontinue study drug administration include, but are not limited to, serious or intolerable AEs suspected to be related to study drug. If dosing is discontinued for systolic BP decreases, or any safety reasons, it should not be restarted. Re-administration of study drug once terminated for safety reasons is not allowed. The total time from initiation of study drug infusion to completion must not exceed 48 hours. In the event that study drug administration is discontinued, regardless of the reason, the patient will continue to be followed at all study visits defined in the protocol.

Changes in study drug dose must be recorded on the Dosage Administration Record CRF.

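### SAP 2.3.5 sets WHF counted from randomization against CBPD groups that form up to about 52 h later, so WHF can be credited to a blood pressure decrease that came after it

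*SAP*

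**What the plan says.** SAP 2.3.5 introduces the analysis with a causal aim: "To further investigate the impact of CBPD, the following analyses will be performed". One item presents CV death through Day 180, WHF through Day 5, and CV death or HF/RF rehospitalization through Day 180 "by CBPD impact on study drug administration (dose decreased or study drug discontinued or both". No reference group, model or test is named for it. The yes/no CBPD split is written only for baseline characteristics and concomitant medications.

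A CBPD is an event of the infusion period. SAP 2.3.5 counts a "confirmed blood pressure decrease requiring a study drug dose adjustment during study drug administration". Protocol 5.5.4 has the infusion start "as soon as possible, but no more than 4 hours after randomization", and Protocol 5.5.5 adds that "The total time from initiation of study drug infusion to completion must not exceed 48 hours". The two responses in Protocol Table 5-4 define the categories: "Reduce the infusion rate by half for the remainder of the study drug administration" or "Permanently terminate study drug infusion".

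The outcomes start earlier. SAP 2.2.2, 2.2.3 and 2.2.6.3 measure all three from randomization. WHF is counted to 120 h, and a death by 120 h without prior WHF counts as a WHF event. Neither document gives a landmark, a time-dependent method, a rule for outcomes that precede the CBPD, or a caution on how to read the table.

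**The concern.** A patient's CBPD category is unknown at randomization and may be settled only about two days later, while outcome events are already accruing. Two problems follow. An event that came before the CBPD appears in the table as if it followed from it. And an event that ends the infusion, or leads to treatment that lowers blood pressure, changes the patient's later chance of being classed as CBPD.

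At stake is how well the trial describes the consequences of a blood pressure decrease, a known effect of the drug for which the protocol has mandatory dose rules. A table meant to show the impact of CBPD could suggest protection, suggest harm, or understate a real harm, purely through the order of events.

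**Working it through.** The plan states no figure for this analysis, so there is none to reproduce. The check uses the plan's own rates and time windows, plus labelled assumptions.

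**1. Time for groups to form.** Start delay 0-4 h (Protocol 5.5.4) plus at most 48 h of infusion (Protocol 5.5.5): 4 + 48 = 52 h after randomization.

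**2. Overlap with the WHF window.** Placebo WHF rate 12.2% through Day 5 (SAP 2.5), constant hazard assumed:
- λ = −ln(1 − 0.122)/120 = 0.001084 per hour
- share of events by 48 h = (1 − exp(−48λ))/0.122 = 0.0507/0.122 = 42%
- share of events by 52 h = 0.0548/0.122 = 45%

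**3. WHF before the CBPD.** Assume CBPD and WHF are unrelated and the infusion continues after WHF. The average CBPD then comes roughly 26 h after randomization (2 h mean delay plus the 24 h midpoint of the infusion). The share of WHF events in CBPD patients that precede the CBPD is about (1 − exp(−26λ))/0.122 = 0.0278/0.122 = 23%. Simulation gives about 22%.

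**4. Effect on the comparison.** Simulation of 4,000,000 patients per scenario, WHF rate as in step 2, start uniform over 0-4 h. Not in the documents and therefore assumed: CBPD incidence (10, 20 or 30% in the first three rows, 20% in the others), the probability q that a WHF event ends the infusion, and any multiplier that WHF puts on the later CBPD hazard. Entries are WHF rate ratios, CBPD to no CBPD.

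| Scenario | Grouped from randomization | Time-dependent CBPD | Landmark 52 h |
|---|---|---|---|
| No effect, q = 0 | 0.99-1.00 | 0.99-1.00 | 0.99-1.00 |
| No effect, q = 0.5 | 0.86-0.88 | 1.00 | 1.00 |
| No effect, q = 1 | 0.72-0.76 | 1.00 | 1.00-1.01 |
| No effect, WHF multiplies CBPD hazard by 1.5 / 2 / 3 | 1.13 / 1.24 / 1.47 | 1.00 | 1.00 |
| True HR 1.5, q = 0 / 0.5 / 1 | 1.39 / 1.24 / 1.11 | about 1.50 | 1.49-1.51 |

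**5. Only the CBPD categories compared.** Assumed: 48 h risk of 15% for a dose decrease and 10% for discontinuation, with the discontinuation hazard tripled after a decrease. With no effect and q = 1, WHF is 10.0% (decrease only), 9.8% (discontinued only) and 9.0% (both), against 12.9% with no CBPD. With q = 0 the figures are 12.2, 12.2, 12.0 and 12.2%.

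**6. The 180-day outcomes.** Placebo CV death 9.0% (SAP 2.5), constant hazard: λ = −ln(0.91)/180 = 0.000524 per day. The share by 48 h is 0.00105/0.09 = 1.2%, and by 52 h 0.00113/0.09 = 1.3%. The simulated no-effect ratio is about 0.996. If 5, 10 or 20% of CV deaths are assumed to fall in the first 52 h, it becomes 0.97, 0.94 or 0.88. For the composite (34.1%), the same formula gives λ = −ln(0.659)/180 = 0.00232 per day and a 52 h share of 0.0050/0.341 = 1.5%.

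**The case against.** **The analysis is supportive.** It sits in the safety evaluation, outside the multiple testing procedure, with no test stated. SAP 2.3.5 already characterizes CBPD onset, blood pressure course, outcome and related AEs, and SAP 2.3.1 compares hypotension events between the treatment groups. All of this stands and limits the weight of the point.

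**No reference group is named.** The ratios in step 4 are for CBPD against no CBPD, a contrast that SAP 2.3.5 does not write for outcomes. That is fair. Step 5 shows that comparing the categories only with each other leaves a smaller distortion, and the missing reference is itself a gap in an analysis of impact.

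**A reader might infer that the bias makes CBPD look safer than it is.** The documents do not fix the direction. The downward route needs WHF to end the infusion; Protocol 5.5.5 allows stopping at the investigator's discretion, but nothing requires it after WHF. The upward route is just as credible. WHF by definition involves intensified IV therapy or mechanical support, which may include IV nitrates (Protocol 6.4.1), and Protocol 5.5.8 urges caution with added treatments that may lower blood pressure.

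**A reader might infer that early deaths seriously bias CV death.** Step 6 does not support that unless deaths cluster early, and the documents give no such figure. A patient who has a CBPD and then dies early is also still in the CBPD group.

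**A reader might infer that Protocol 3.6 rests on the same flaw**, since it says of patients with a blood pressure decrease that "worse outcomes were not observed in these patients". The documents do not say how that comparison was made, and the section also relies on monitoring and on the dose rules. It shows only that outcomes after a decrease inform the benefit-risk argument.

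**Conclusion.** The point holds for WHF through Day 5. Between 42 and 45% of the WHF events fall while the CBPD groups are still forming, and about 22% of those in CBPD patients would precede the CBPD if the two were unrelated. The overlap rests on the planned 12.2% rate and a constant hazard. The size of the bias rests on assumed CBPD incidence and assumed links between WHF and CBPD: a ratio of 0.72 to 1.47 with no true effect, and a true 1.5 reduced to 1.11-1.39. If WHF neither ends the infusion nor changes the CBPD risk, there is practically no bias under no effect, only misattributed events and dilution of a real one.

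For the 180-day outcomes the overlap is only 1.2-1.5% of events under a constant hazard. The primary tests and the type I error are not affected. This is a cheap improvement to a supportive safety analysis.

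**What to change.** In SAP 2.3.5:

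- Name no CBPD as the reference group.
- Analyse the three outcomes with CBPD status (none, dose decreased, discontinued, both) as a time-dependent covariate in a Cox model. This keeps every event and assigns it to the patient's status at that time.
- Show WHF events before and after the CBPD separately.
- As a sensitivity analysis, use a landmark at the end of the infusion window, about 52 h after randomization, in patients alive and, for WHF, event-free. State that it drops about 45% of WHF events under a constant hazard, including those during the infusion itself. A landmark 48 h after randomization would come too early for patients whose infusion started late.
- State that the results are descriptive, because neither method removes confounding between patients with and without a CBPD.

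No new data are needed. SAP 2.3.5 already summarizes CBPD onset relative to the start of study drug, SAP 2.1.9 summarizes the delay from randomization to study drug, and Protocol 6.3 records infusion times and rates. The cost is SAP wording and a little more analysis work.
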